**Confidential**

---

 For some tests associated with BILAG, samples will be collected and sent to the central laboratory. The analysis of the sample will only be done upon request of the investigator. The following blood tests must be performed at Day 1 pre-dose but are optional at all other visits: cardiolipin IgA, IgG and IgM antibodies and lupus anticoagulant. Haptoglobin is optional at all visits.

 Only applicable for WoCBP. The serum pregnancy test at Visit 1 must be performed at least 3 weeks before the urine dipstick pregnancy test performed at Visit 2.

 All AEs and SAEs that occur after signing the informed consent form and up to 6 months after study treatment discontinuation must be reported.

 Study treatment should be administered at the site from study treatment dispensed on the day of the visit, after study assessments have been performed.

 Ophthalmological examination and OCT may be performed up to 7 days prior to the visit date but no later than 7 days after the visit.

 All participants will be asked to return for an EOT visit. For participants who permanently discontinued study treatment, the pEOT visit will occur within 7 days of last intake of study treatment and participants will thereafter attend PTOP visits [see Table 3]. If a pEOT visit occurs within 7 days of a scheduled PTOP visit, this PTOP visit should be skipped. For all other participants, the EOT visit will coincide with Visit 14.

 After completion of the Month 12 visit, participants will be asked to complete the follow-up period.

 For Visits 16–19, the site will dispense urine pregnancy kits to WoCBP and collect the results during the scheduled phone call. If a urine test is positive, the participant will be instructed to return to the site for a serum pregnancy test.

 During unscheduled visits, any additional assessments considered necessary by the investigator may be performed.

AE = adverse event; ANA = antinuclear antibodies; anti-dsDNA = anti-double-stranded deoxyribonucleic acid; BILAG = British Isles Lupus Assessment Group-2004; bpm = beats per minute; CLASI = Cutaneous Lupus Erythematosus Disease Area and Severity Index; DBP = diastolic blood pressure; ECG = electrocardiogram; eCRF = electronic case report form; EDTA = ethylenediaminetetraacetic acid; EOT = End-of-Treatment; FSV = final study visit; FU = follow-up; IFN-1 = Type 1 interferon; IRT = Interactive Response Technology; mSLEDAI-2k = modified Systemic Lupus Erythematosus Disease Activity Index-2000; OCT = optical coherence tomography; pEOT = premature End-of-Treatment or permanent discontinuation of study treatment; PGA= Physician's Global Assessment; PK = pharmacokinetic; PTOP = post-treatment observation period; RI = re-initiation; SAE = serious adverse event; SBP = systolic blood pressure; SFI = SLE Flare Index; SLE = systemic lupus erythematosus; SLEDAI-2K = Systemic Lupus Erythematosus Disease Activity Index-2000; TB = tuberculosis, WoCBP = women of childbearing potential.

Confidential

**Table 3 Schedule of activities: PTOP (applicable to participants who permanently discontinue study treatment**

PERIODS	Name		POST-TREATMENT OBSERVATION		
	Duration	Up to 12 months 	Up to 6 months 		
PTOP VISITS 	Number	PTOP 3, 4, 6, 7, 9, 10, 12, 13 	PTOP 5, 8, 11, 14 	PTOP 15 	PTOP 16, 17, 18, 19 
	Name	Months 1, 2, 4, 5, 7, 8, 10, 11	Months 3, 6, 9, 12	FU Month 1	FU Months 2, 3, 4 and 5 Phone call
	Time window	Days 30, 60, 120, 150, 210, 240, 300, 330 (±7 days)	Days 90, 180, 270, 360 (±7 days)	1 month after last dose (±7 days)	Monthly after PTOP FU1 (±7 days)
To be performed at all visits					
Pregnancy test 	X	X	X	X	X
SAEs/AEs	X	X	X	X	X
SLE concomitant therapies	X	X	X	X	X
To be performed at specific visits					
Physical examination	X	X	X		X
Body weight 	X	X (Month 12)			X
mSLEDAI-2K, BILAG, SFI, PGA, CLASI, tender/swollen joint count,	X	X			
Vital signs, 12-lead ECG	X	X	X		X
Ophthalmological examinations		X (Months 3, 6, 12)			X
OCT		X (Months 3, 12)			
Labs (hematology/blood chemistry, urine analyses) 	X	X	X		X
Anti-dsDNA, complement (C3, C4, CH50)	X	X			X
ANA		X			X
Anti-Smith					X

 Participants who permanently discontinue study treatment will attend PTOP visits starting at the visit following the permanent treatment discontinuation as follows:

- Participants who permanently discontinue before or at Month 6 will complete study visits until Month 12 and the FSV will be at Month 12 (i.e., PTOP Visit 14).
- Participants who permanently discontinue between Month 7 and Month 12 (both inclusive), will complete PTOP FU visits until at least 6 months after last study treatment intake and the FSV will be one of the monthly PTOP FU visits, as applicable.

**Confidential**

 Only applicable for WoCBP. A serum pregnancy test for participants who permanently discontinue study treatment before or at Month 6 will be performed and analyzed centrally at Month 12 (i.e., PTOP Visit 14). A serum pregnancy test for participants who permanently discontinue study treatment between Month 7 and Month 12 (both inclusive) will be performed and analyzed centrally at FSV, i.e., 6 months after last study treatment intake. Urine pregnancy tests will be performed at all other visits with kits provided by the site.

 Body weight should be measured as part of BILAG assessment at each applicable visit and recorded in the source documentation. It should also be recorded in the eCRF at PTOP 14 and 20.

 A central laboratory will be used for all protocol-mandated laboratory tests, including retests due to laboratory abnormalities and laboratory tests performed at unscheduled visits.

AE = adverse event; ANA = antinuclear antibodies; anti-dsDNA = anti-double-stranded deoxyribonucleic acid; BILAG = British Isles Lupus Assessment Group-2004; CLASI = Cutaneous Lupus Erythematosus Disease Area and Severity Index; ECG = electrocardiogram; eCRF = electronic case report form; FU = follow-up; FSV = final study visit; mSLEDAI-2k = modified Systemic Lupus Erythematosus Disease Activity Index-2000; OCT = optical coherence tomography; PGA = Physician's Global Assessment; PTOP = post-treatment observation period; SAE = serious adverse event; SFI = SLE Flare Index; SLE = systemic lupus erythematosus; SLEDAI-2K = Systemic Lupus Erythematosus Disease Activity Index-2000; WoCBP = women of childbearing potential.

## 2 INTRODUCTION

### 2.1 Indication

#### Systemic lupus erythematosus

SLE is an autoimmune disease of unknown etiology, characterized by the production of pathogenic autoantibodies, tissue deposition of immune complexes, and tissue damage across multiple organ systems. This heterogeneous, chronic, debilitating, autoimmune inflammatory disorder characterized by diverse clinical manifestations can affect any organ or system in the body simultaneously or sequentially [Kaul 2016]. The adaptive T and B cells and the innate immune system are considered to play a major pathophysiological role in this disease [Carroll 2004, Kaul 2016].

Despite many treatment advances and improved diagnostics, SLE continues to cause substantial morbidity and premature mortality. Current management strategies are limited by high failure rates and toxicity. An overreliance on CS therapy contributes to much of the long-term organ damage [Durkan 2019].

#### Medical need for new targeted therapies

The current treatment of SLE comprises NSAIDs, antimalarials, CS, and immunosuppressive drugs, often prescribed in that order as the disease progresses [Xiong 2014]. Belimumab (an inhibitor of soluble B-cell-activating factor), approved by the FDA in 2011, anifrolumab (an IFN-1 receptor antagonist), approved by the FDA in 2021, and telitacicept (a novel human recombinant fusion protein) conditionally approved in China in 2021 are the only treatments approved for SLE in over 60 years [Furie 2019, Morand 2020, Navarra 2011, Dhillon 2021]. Clinical experience with anifrolumab and telitacicept is limited to date. Other medications currently used to treat SLE, such as azathioprine, cyclophosphamide, and mycophenolate mofetil / mycophenolic acid, have not been approved for the disease by regulatory authorities. Antimalarials and CS are also used to control some manifestations of lupus (e.g., arthralgia, arthritis, and rashes). All these drugs have well-documented and substantial safety profiles and are not effective in all patients and/or on all SLE manifestations. Furthermore, it is difficult to taper participants with moderate or severe disease completely off CS, which cause long-term morbidity and may contribute to early cardiovascular mortality [Petri 2001, Urowitz 1976]. Even small daily doses of 5 to 10 mg prednisone used long term carry increased risks of side effects such as cataracts, osteoporosis, and coronary artery disease [Petri 2001].

In China there is a large population of SLE patients with a clinical presentation that may differ from that reported in other ethnicities [Tian et al 2022]. Guidelines developed by Chinese rheumatologists and other experts have made several recommendations for the diagnosis, treatment and follow-up of disease activity, including disease monitoring using the SLEDAI-2K which will be used in this clinical study [Li et al 2020]. It has been shown

that Chinese SLE patients that experience severe flares have associated costs 5 times greater than those with non-severe flares [He et al 2023]. This suggests that aside from the medical rational to reduce flares and thus subsequent organ damage there is also an economic reason.

There is thus a medical need to identify new targeted therapies, particularly agents that may reduce the requirement for CS and cytotoxic agents.

Though recent improvements in care have dramatically enhanced the survival of patients with SLE, increased morbidity and mortality remain a major concern. Many patients have partially controlled disease and progression to end-stage organ involvement continues, and the therapies carry risks of debilitating side effects [Lateef 2012]. Therefore, it is important to continue the development of medical products that have the potential to be more effective and/or less toxic.

## 2.2 Investigational treatment

Cenerimod is a potent, orally active, selective S1P1 receptor modulator that blocks the egress of lymphocytes from lymphoid organs and thus reduces the tissue availability of circulating lymphocytes (T and B cells). This PD effect, observed in both healthy volunteers and SLE patients, is sustained with continued daily oral dosing. After study treatment discontinuation, a gradual return towards baseline levels in lymphocyte counts was observed [Cenerimod IB, Hermann 2019]. The compound was selected based on its potential for o.d. oral administration, its long  $t_{1/2}$  allowing a built-in natural up titration, and its high selectivity for the S1P1 receptor [Juif 2016, Juif 2017].

Cenerimod has unique S1P1 receptor-signaling properties, and an improved safety profile compared to other S1P modulators. For instance, the absence of broncho- and vaso-constrictor effects ex vivo and in vivo was notable [Piali 2017]. Cenerimod dose-dependently lowered circulating lymphocyte counts in animal models (mice, rats, dogs) and in human participants, leaving Natural Killer cell and monocyte counts unaffected. Cenerimod effectively attenuated disease variables in a mouse experimental autoimmune encephalitis model and was effective in the treatment of lupus-like disease in the MRL/lpr mouse model of SLE [Cenerimod IB, section 1.3.1].

The PK of cenerimod in healthy participants were characterized by a slow absorption (median  $t_{max}$ : 5–6 and 6–7 h after single- and multiple-dosing, respectively) and elimination ( $t_{1/2}$  approximately 33 days measured after the last dosing under steady-state conditions), dose-proportional exposure in the range of 0.5–4 mg, and steady-state conditions reached within 50 days. Cenerimod showed an accumulation of approximately 8-fold at steady state when compared to the first day of treatment. The PK of cenerimod support o.d. dosing and no dose adjustment is required for sex, ethnicity, or fed/fasted state. Cenerimod can be concomitantly administered with drugs that are inhibitors, inducers, or substrates of

cytochrome proteins without dose adjustment. Further details on the PK characteristics of cenerimod are provided in the IB [Cenerimod IB].

The first study performed in adult participants with moderate-to-severe SLE (AC-064A201) met its primary objective by establishing the dose-response relationship of cenerimod based on the reduction of lymphocyte count in peripheral blood. The AC-064A201 study demonstrated that cenerimod significantly reduced lymphocyte counts in a dose-dependent manner ( $p < 0.01$ ) as expected from its primary mode of action [Cenerimod IB, sections 1.4.2.2 and 5.3.1.1]. The exploratory analysis of efficacy suggested clinical improvement, particularly with the higher cenerimod doses [Cenerimod IB, section 5.3.1.1]. Cenerimod treatment was well tolerated in patients with SLE at all doses tested [Cenerimod IB, section 5.3.2.2].

In adult participants with moderate-to-severe SLE (Phase 2b study ID-064A202), cenerimod 4 mg showed a clinically significant reduction in disease activity characterized by an improvement in the mSLEDAI-2K score from baseline to Month 6 (the primary efficacy endpoint). [Cenerimod IB, sections 1.4.3 and 5.3.1.2]. The subgroup analyses of change from baseline to Month 6 in mSLEDAI-2K in participants with a more severe or more active disease categorized by daily dose of CS ( $\geq 7.5$  mg/day) and by mSLEDAI-2K score ( $\geq 10$ ) at baseline revealed that efficacy of the 4 mg dose appeared to be greater (vs placebo and lower doses) in participants receiving higher doses of prednisone or with a more active disease. [Cenerimod IB, section 5.3.1.2]. The cenerimod safety profile did not show any unexpected findings and safety areas of special interest related to class did not raise any concerns with any dose, up to and including 4 mg [Cenerimod IB, section 5.3.2.3].

Post-hoc analyses were made by immunological status at baseline with regards to IFN-1, anti-dsDNA, and complement C4 and C3 levels at baseline. The placebo-corrected changes in mSLEDAI-2K score for the cenerimod 4 mg dose were consistently larger compared to placebo in participants with high disease activity assessed by the immunological variables. Based on these data, the same analytes will be measured in this clinical study to compare the results with previous studies.

In participants with high IFN-1 status at entry, representing 50.7% of the overall study population, the placebo-corrected mSLEDAI-2K change from baseline to Month 6 in participants on cenerimod 4 mg was greater than that observed in the overall population.

## 2.3 Study rationale

Despite recent improvements in treatment regimens and medical care in reducing mortality and morbidity, many patients have partially controlled disease and progression to end-stage organ involvement, and the therapies carry risks of side effects [Lateef 2012]. Effective control of SLE is still difficult due to disease heterogeneity and variability in disease manifestations among individuals.

Results of recently conducted clinical studies in SLE patients have demonstrated a favorable effect of cenerimod on mediators of inflammation and on lupus efficacy clinical outcome measures [see Section 2.2]. In the Phase 2b dose-finding study (ID-064A202), cenerimod 4 mg was well tolerated over a treatment period of 6 months with limited side effects vs placebo.

The nonclinical safety data and the resulting safety margins / exposure ratios are considered adequate to support the safe use of cenerimod in humans at the dose of 4 mg selected for the ID-064A204 study.

Cenerimod exposure in the Chinese population has not yet been evaluated and, while differences in drug response due to intrinsic or extrinsic factors in the Chinese ethnic population are not expected based on cenerimod properties, it should be assessed. For Chinese participants, a staggered approach will therefore be implemented with the limited ID-064A204 study started first to mitigate the risk of exposing a large number of Chinese patients to cenerimod 4 mg. Study ID-064A204 will evaluate the safety, tolerability, PK and PD of cenerimod in Chinese participants.

The safety of the participants will be closely monitored and safety review will be conducted regularly and on demand.

## 2.4 Benefit/risk assessment of cenerimod

Currently there is limited clinical data to assess the benefit/risk ratio of cenerimod. In the following sub-sections, the potential and known risks and potential benefits of treatment with cenerimod are discussed.

### 2.4.1 Potential benefits

In the Phase 2b study (ID-064A202), the primary analysis of efficacy at 6 months revealed a clinically and nominally statistically significant improvement ( $p = 0.029$ ) in mSLEDAI-2K score from baseline to Month 6 in cenerimod 4 mg vs placebo. From Month 4 onwards, the change from baseline and the difference to placebo was consistently larger in the cenerimod 4 mg group than for lower doses and placebo. For the secondary endpoints, a numerically greater response in SRI-4 was observed at Month 6 in the 4 mg group than in the placebo group. The effect was greater in participants with more serologically or clinically active disease. The selection criteria for the population in the current study are aimed at enrolling a population with a clinically and serologically active disease, as this population will potentially derive greater benefit from treatment.

Based on available data, cenerimod may have the potential to be a new oral therapeutic approach for patients with SLE [see Cenerimod IB, section 5.3].

## 2.4.2 Known and potential risks

Safety areas of special interest were identified in the nonclinical program and were considered in the clinical development of cenerimod. Compared to other S1P receptor modulators, the S1P1-selective cenerimod did not show a negative effect on bronchoconstriction or vasoconstriction, which are known class effects; the spirometry data showed no significant worsening of the pulmonary function in participants treated with cenerimod compared to placebo. Nonclinical pharmacological studies concluded that the QT prolongation potential of cenerimod is low; this was later confirmed in humans [Cenerimod IB, section 5.3.2.1.3]. Furthermore, the results of the ECG monitoring and echocardiography sub-study performed during the ID-064A202 study were not suggestive of any clinically relevant effect in humans.

Accordingly, and taking into consideration the safety results from the Phase 2b study (ID-064A202), the following risk-minimization measures for identified and potential risks will be implemented for participants participating in this study:

### Identified risks:

- Cardiovascular variables: cenerimod shows a transient effect on HR at the time of first dose intake, with a maximum decrease of 9 beats per minute (bpm) observed 6 h post-dose. To mitigate the risk of cardiac events, participants will be excluded from this Phase 2 study if they have certain cardiac rhythm disorders, ECG abnormalities indicative of increased risk for arrhythmia, and/or low resting HR [see Section 5.3]. Participants will be excluded or discontinued if receiving medications likely to reduce HR (e.g., beta-blockers) or to increase the risk of cardiac arrhythmia [see Sections 5.3 and 6.2.3]. All participants in this clinical study will undergo cardiac monitoring on Day 1 for 12 hours. Since the effects on HR are expected to be transient and related to initial dosing, no treatment of sinus bradycardia and/or atrioventricular (AV) block is anticipated, unless the symptoms or the seriousness of the condition mandate therapeutic intervention in the view of the treating physician.

### Potential risks:

- Embryo-fetal animal toxicity studies showed that cenerimod is embryotoxic and teratogenic in rats and rabbits. Therefore, pregnant women are excluded from this study [see Section 5.3]. Cenerimod should be given to WoCBP only when the absence of pregnancy has been verified, appropriate advice on contraception has been provided, and highly effective contraception is practiced [see Section 5.5]. Women should not become pregnant while on treatment and for 6 months after discontinuation of cenerimod. During these periods, the absence of pregnancy is monitored monthly [see Table 2]. Occurrence of pregnancy will result in immediate discontinuation of the study treatment and monitoring of the pregnancy [see Section 5.8.1.2].

- Liver: a slightly higher incidence of hepatic AEs (mostly denoting liver enzyme increase) and liver enzyme marked abnormalities with no dose-related trends were observed in participants treated with cenerimod compared to placebo in the ID-064A202 study [Cenerimod IB, section 5.3.2.3]. Overall, the incidence of hepatobiliary disorders was lower than seen with other S1P receptor modulators. Participants with signs of ongoing liver disease will not be enrolled into this study and monitoring/discontinuation criteria are applied [see Sections 5.3 and 5.8.1.7].
- Abnormal Immunomodulation: cenerimod reduces the number of circulating lymphocytes. Because of reduced immune surveillance, the risk of infections and malignancy may be increased. Participants with low lymphocytes and/or presenting certain types of malignancies at Screening are excluded from this study [see Section 5.3]. Monitoring/discontinuation criteria are applied [see Section 5.8.1.6].
- Infections: heightened vigilance is required for opportunistic infections, particularly for potentially serious viral infections with neurological symptoms, such as reactivation of human herpes viruses, and of John Cunningham polyoma virus, the causative agent of progressive multifocal leukoencephalopathy. If findings raise suspicion of an opportunistic infection, the participant must discontinue the study treatment. Study -specific eligibility/discontinuation criteria and proper clinical monitoring are applied in the study [see Sections 5.3 and 5.8.1.5]. Results from the ID-064A202 study did not reveal an increased rate of infection in participants treated with cenerimod compared to placebo [Cenerimod IB, section 5.3.2.3].
- Vaccination: no clinical data are currently available on vaccination efficacy under cenerimod. The currently registered S1P receptor modulators (i.e., fingolimod, siponimod, ozanimod, ponesimod) may reduce vaccine effectiveness [Gilenya® SmPC, Mayzent® SmPC, Ponvory® SmPC, Zeposia® SmPC ]. Patients with SLE hospitalized because of COVID-19 have significantly higher risks of death and poor outcomes than patients without comorbidities and patients with other comorbidities [Bertoglio 2021]. COVID-19 vaccination induced humoral and cellular responses against SARS-CoV-2 variants in SLE [Moyon 2021] and appears well tolerated in patients with SLE, with only a minimal risk of flare, if any, including after the mRNA vaccines [Felten 2021]. Altogether, vaccination of participants participating in this study may be recommended by the investigator, except for vaccination with live vaccines, which is not allowed within 30 days prior to Day 1 and up to 6 months post last study dose.
- Macular edema: clinical experience with other S1P receptor modulators indicates that participants treated with these drugs may be at increased risk of developing macular edema. Participant safety is ensured by implementation of appropriate eligibility and discontinuation criteria as well as monitoring during this study [see Sections 5.3 and 5.8.1.8]. Participants presenting with a suspicion of macular edema, as reported by

investigators, will be temporarily discontinued from study treatment while an IOSB reviews and assesses the suspected cases [see Section 4.4].

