### 5.8.1 Study treatment interruption and permanent discontinuation of study treatment

#### 5.8.1.1 Principles

The decision to permanently discontinue the study treatment can be made by the participant, the investigator/delegate, or the sponsor personnel.

The investigator/delegate has the option of temporarily interrupting or permanently discontinuing the study treatment for a given participant in response to an AE, a diagnostic or therapeutic procedure, a laboratory abnormality, or for administrative reasons. If the

study treatment is interrupted by the participant for any reason, he/she must inform the investigator/delegate as soon as possible. Any study treatment interruptions (i.e., for a day or more) must be recorded in the eCRF.

The investigator/delegate must permanently discontinue the study treatment for a given participant if, on balance, he/she believes that continued administration would be contrary to the best interests of the participant.

Study-specific criteria for temporary interruption and permanent discontinuation of the study treatment are described in Sections 5.8.1.2 to 5.8.1.11.

The main reason for permanent discontinuation of the study treatment (e.g., due to pre-specified study treatment discontinuation criteria, an AE, lack of efficacy, study termination) must be documented in the eCRF.

A participant who permanently discontinues the study treatment is **NOT** considered withdrawn from the study. The participant will be asked to return for a pEOT visit within 7 days after the last dose of study treatment intake, and thereafter to attend further planned visits as defined in the SoA [Table 2 and Table 3] and in Section 7.2.

All participants withdrawn from study treatment are encouraged to continue the planned study procedures (e.g., visits and questionnaire completion [Table 3]) until planned FSV, provided that the participant's consent for this further limited participation in the study has not been withdrawn. This will decrease the amount of missing data, which is important to maintain the integrity of the study.

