### **5.8.1.5 *Infections***

In the event of a serious infection as per the investigator's opinion (e.g., opportunistic infection or serious infection requiring i.v. medication or hospitalization), the participant should be adequately treated and monitored until resolution of the infection. The investigator should consider permanent discontinuation of study treatment. The decision to

permanently discontinue study treatment should be made after evaluation of all available information concerning all potential causes of infection and based on the clinical status of the participant and response to the treatment of the infection. Further diagnostic work-up and consultation with an infectious disease specialist or other specialist should be considered according to local practice and the clinical situation.

These AEs must be reported in the eCRF [see Section 8.2]. Concomitant immunomodulatory medications may also be discontinued at the discretion of the investigator.

**Note:** Participants should not receive any of the per-protocol prohibited systemic treatments during 6 months after last study treatment intake, unless clinically indicated and justifiable in the opinion of the investigator.

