### Re-test result is $< 100$ cells/ $\mu$ L (i.e., $0.1 \times 10^9$ cells/L or $0.1 \times 10^3$ cells/ $\mu$ L)

The participant must be permanently discontinued from study treatment, except at the first occurrence of a total lymphocyte count at re-test  $< 100$  cells/ $\mu$ L, in which case the participant must be re-tested within 1 week. Then, based on the results:

- If the lymphocyte count at 1-week re-test is confirmed  $< 100$  cells/ $\mu$ L, the participant must be permanently discontinued from study treatment. For results of 100 to  $< 200$  cells/ $\mu$ L or  $\geq 200$  cells/ $\mu$ L, see instructions above.

**Note:** If the lymphocyte count  $< 200$  cells/ $\mu$ L is accompanied by signs of opportunistic infection or severe infection (as per investigator's judgment), the study treatment will be permanently discontinued. The participant will be medically followed [see Section 5.8.1.5].

**Figure 2** Guidance for re-test results of lymphocytes  $< 200$  cells/ $\mu$ L

[figure not shown]

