#### **5.8.1.9 *Initiation of forbidden concomitant medication during the study***

At any time throughout the study, study treatment will be permanently discontinued if the participant starts taking a forbidden concomitant therapy [see Section 6.2.3].

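### Section 2.4.2 requires study treatment to stop on a suspected opportunistic infection, but at 200 cells/µL or above the stopping criteria in Section 5.8.1 leave this to the investigator

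*Combined protocol and SAP*

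**What the plan says.** Section 2.4.2 introduces its list of risks by saying that "the following risk-minimization measures for identified and potential risks will be implemented for participants participating in this study". Its Infections bullet then gives the rule: "If findings raise suspicion of an opportunistic infection, the participant must discontinue the study treatment". The bullet refers to Sections 5.3 and 5.8.1.5 for the eligibility and discontinuation criteria. It does not cite Section 5.8.1.6.

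Section 5.8.1.1 tells the site where the operative rules are: "Study-specific criteria for temporary interruption and permanent discontinuation of the study treatment are described in Sections 5.8.1.2 to 5.8.1.11". For adverse events in general it is permissive: "The investigator/delegate has the option of temporarily interrupting or permanently discontinuing the study treatment for a given participant in response to an AE".

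Section 5.8.1.5 covers infections that the investigator regards as serious and gives opportunistic infection as an example. Its instruction on study treatment is: "The investigator should consider permanent discontinuation of study treatment". That decision comes after the possible causes, the participant's condition and the response to anti-infective treatment have been assessed.

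Section 5.8.1.6 ends its re-test guidance with a Note: if a lymphocyte count below 200 cells/µL "is accompanied by signs of opportunistic infection or severe infection (as per investigator's judgment), the study treatment will be permanently discontinued". The Note refers back to 5.8.1.5.

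**The concern.** Two parts of the same protocol give instructions of different strength for the same safety event. An investigator who suspects an opportunistic infection and goes to 5.8.1.5, as both 2.4.2 and 5.8.1.1 direct, finds a decision to weigh and no instruction to stop or hold the drug in the meantime. One who relies on 2.4.2 stops at once.

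The drug lowers circulating lymphocytes and is given on top of background therapy that may itself be immunosuppressive. Section 2.4.2 asks for heightened vigilance for serious viral infections with neurological symptoms. At stake are participant safety and uniform conduct across 5 to 10 sites. Following 5.8.1.5 as written could leave a participant on treatment when the protocol's own risk measure requires a stop.

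**Working it through.** No figure in the plan bears on this point, so the check is a comparison of the rules.

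**Step 1. The two sections side by side.**

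| | Section 2.4.2 | Section 5.8.1.5 |
|---|---|---|
| Trigger | Findings that raise suspicion | An infection serious in the investigator's opinion; opportunistic infection is an example |
| Force | Mandatory | Advisory |
| Timing | On suspicion | After evaluation |
| Hold during work-up | Implied by the stop | None stated |
| Lymphocyte condition | None | None |

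They differ in force and in timing.

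**Step 2. Other listed criteria that could supply the missing stop.** Sections 5.8.1.2 to 5.8.1.11 cover pregnancy, contraception, cardiovascular findings, infections, lymphocyte count, liver tests, ocular findings, forbidden medication, malignancy and re-initiation. Only 5.8.1.5 and the 5.8.1.6 Note deal with infection directly. The Note is mandatory and permanent but conditional on the count.

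**Step 3. The resulting rule by lymphocyte count, for a suspected opportunistic infection.**

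- Below 200 cells/µL: the Note requires a permanent stop. This broadly agrees with 2.4.2, although the Note is triggered by signs of infection and 2.4.2 by suspicion.
- 200 cells/µL or above: among the listed criteria only the advisory wording of 5.8.1.5 addresses the infection. This conflicts with 2.4.2.

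Exclusion criterion 24 bars a screening count below 500 cells/µL. Every eligible participant therefore enters, on the screening count, in the range where the Note does not apply. The documents do not say how many move below 200 cells/µL on treatment.

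**Step 4. How the protocol handles other events that call for action before confirmation.** For suspected macular edema, 2.4.2 describes a temporary stop, and 5.8.1.8 repeats it as a mandatory interruption while the case is assessed. For a positive urine pregnancy test, 5.8.1.2 requires immediate interruption until the serum result is known. In both cases the operative section carries the rule. For opportunistic infection it does not, which looks like an omission.

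**Step 5. What can be sized.** The frequency cannot. There is no opportunistic infection rate, no on-treatment lymphocyte distribution, and a planned enrolment of about 15 (Section 9.4).

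**The case against.** The strongest reply is that the protocol already has a mandatory stop in the very next section. The 5.8.1.6 Note is cross-linked to 5.8.1.5, and the 2.4.2 bullet immediately before Infections mentions the risk of infection and cites 5.8.1.6. This stands. A reader might infer that the protocol has no mandatory infection stop at any lymphocyte count; the Note shows otherwise. The gap is confined to 200 cells/µL or above.

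Second, the sections can be read in sequence: stop on suspicion under 2.4.2, then decide on permanence under 5.8.1.5. Section 2.4.2 does not call the stop permanent, and discontinuation can be temporary in its vocabulary: suspected macular edema cases "will be temporarily discontinued from study treatment while an IOSB reviews and assesses the suspected cases". This reading is reasonable and probably close to what was intended. But 5.8.1.5 does not contain the first step, and 5.8.1.1 makes interruption for an adverse event optional.

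Third, 2.4.2 is itself protocol text. A reader might infer that the rule is absent from the protocol, and that would be wrong. It is present but missing from the section that lists the stopping criteria.

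Fourth, other safeguards exist. Section 5.8.1.1 requires permanent discontinuation when continuing would be against the participant's interests, and the sponsor reviews safety continuously (Section 10.9). The first depends on investigator judgment, and the second sets no stopping rule. In addition, under 5.8.1.9 "study treatment will be permanently discontinued if the participant starts taking a forbidden concomitant therapy", and Appendix 4 includes several antibacterials and antifungals. It lists no antiviral, however, so antiviral treatment of a suspected herpes virus reactivation, an example given in 2.4.2, would not trigger a stop through that list.

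Finally, 2.4.2 reports no increased infection rate against placebo in the Phase 2b study. That bears on how often the question will arise, not on which instruction applies when it does.

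**Conclusion.** The inconsistency is real but limited. For a suspected opportunistic infection with a lymphocyte count of 200 cells/µL or above, 2.4.2 mandates a stop, while the stopping section it cites leaves the matter to judgment and provides no hold during work-up. Below 200 cells/µL the protocol is broadly consistent.

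This is an internal inconsistency in a safety rule and should be fixed. It does not alter any planned analysis or the sample size. The conclusion rests on the wording alone and on the assumption that sites will treat 5.8.1 as the operative list, as 5.8.1.1 tells them to. The documents do not support a claim that participants face a measurable excess risk because of it.

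**What to change.** Add to 5.8.1.5 a rule to this effect: when an opportunistic infection is suspected, study treatment must be interrupted immediately whatever the lymphocyte count; it may resume only if opportunistic infection is ruled out; and it must be permanently discontinued if the infection is confirmed. Reword 2.4.2 to match, so that it is clear whether the stop is an interruption or permanent, and cite 5.8.1.6 in its Infections bullet. Keep the permanent stop below 200 cells/µL. Because suspicion remains a matter of judgment, some difference between sites would persist; repeating in 5.8.1.5 the examples given in 2.4.2 would reduce it.

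Softening 2.4.2 to match 5.8.1.5 and 5.8.1.6 would also restore consistency, but it would weaken a stated risk-minimization measure.

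The change takes a few lines at the next amendment and needs no new procedure. Section 5.8.1.1 already requires interruptions of a day or more to be recorded, and 5.8.1.11 requires a re-initiation visit only for gaps of more than 7 consecutive days between Day 1 and Day 14. Version 3.0 reports no participants enrolled, so a prompt change could precede most exposure.

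The cost is missed doses for suspicions later ruled out. Before Month 2 this could disturb that participant's only scheduled full steady-state profile, which supplies the steady-state AUC and the accumulation index, and might remove the participant from the PK analysis set (Section 9.1.3). With 15 planned, one participant is 1/15 = 6.7% of the sample. That is a modest price for a clear stopping rule.
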